- 5. Proportion of patients actively on OAC at 12 months of follow-up
- 6. Incident rate of hospitalization for any bleeding
- 7. All-cause in-hospital mortality rates
- 8. All-cause mortality rates among patients with accurate out-of-hospital mortality data (such as Medicare Advantage patients)
- 9. Health care utilization for AF patients, which would be reported as counts of number of health care utilization events (outpatient visits, days hospitalized, number of emergency department visits, etc.)

C. EXPLORATORY OBJECTIVES

The exploratory objectives are to:

- 1. Evaluate the effect of the early and delayed education interventions on primary and secondary endpoints over the course of the follow-up through the date on which at least 80% of eligible study participants have at least 24 months of follow-up time.
- 2. Explore the CTTI and the FDA supported Sentinel Data Partnership's ability to successfully conduct a pragmatic trial to answer important questions to improve public health.

VI. STUDY DESIGN AND DURATION

The study is a prospective, randomized, and open-label education intervention trial. Patients with AF and a CHA₂DS₂-VASc score of 2 or greater will be randomized in a 1:1 ratio to an early intervention cohort and a delayed intervention cohort within each participating health plan. The definition for OAC medication fill will be an OAC medication dispensing or at least 4 INR tests in the claims data.¹ The claims records of the patients randomized to the early intervention cohort will then be linked to "fresh" (i.e. about 1-4 months old) pharmacy claims data at the time of randomization. Patients without evidence of an OAC medication fill during the 12 months prior to randomization will be included in the patient-level and provider-level early educational intervention (patients randomized to this early intervention with evidence of an OAC medication fill during the 12 months prior to randomization will be excluded from the trial.). In addition to usual care, these patients and their providers² will receive a

¹Not all OAC dispensings are well captured in pharmacy claims, particularly, for warfarin. INR tests are assumed indicative of OAC fills that were not billed through the claims. 4 INR tests or values within a 12-month period will be used as a proxy since that is roughly the number of tests administered in the process of stabilizing dose.

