- 2. Time to OAC start: the time to first OAC initiation, as defined by the first fill date for apixaban, dabigatran, edoxaban, rivaroxaban, or warfarin. If there was no prescription fill for these medications, but the patient had 4 or more INR values measured over the study period, the date of the first INR measurement will be used for initiation of OAC.
- 3. OAC prescription coverage: the proportion of days that AF patients have OAC prescription fills over the duration of the study. The assumption is that a 30-day or 90-day supply will last for the planned period, even in the case of warfarin, when the length of time that a prescription lasts may be less well defined. Patients will only be included in this secondary analysis, if they had a prescription fill for apixaban, dabigatran, edoxaban, rivaroxaban, or warfarin.
- 4. OAC rates at follow-up: proportion of patients with an active oral anticoagulant dispensing at the end of the one-year follow-up. This will include patients with apixaban, dabigatran, edoxaban, rivaroxaban, or warfarin medication fills that encompass the end of the study period. If there was no prescription fill for these medications, this will also include patients with 4 or

more INR values measured over the study period, who had an INR value measured within 60 days of the end of the approximately one-year follow-up.

- 5. Rate of stroke or TIA: the incident rate of stroke or TIA related hospitalizations; stroke, excluding transient ischemic attacks (TIAs), will also be assessed
- 6. Rate of bleeding related hospitalization: the incident rate of hospitalizations for any bleeding
- 7. Health care utilization: the total counts of health care utilization (number of outpatient visits, emergency department visits, hospital admissions, etc.) for AF patients, including AF and non-AF related care
- 8. In-patient all-cause mortality: patients with in-hospital death
- 9. All-cause mortality: in a subset of patients with mortality status

XVI. STATISTICAL ANALYSES

A. DEMOGRAPHICS AND BASELINE CHARACTERISTICS

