[figure not shown]
Details on the analyses are provided in Section II. Here we describe the data sources for the **modified intention-to-treat** (primary) and **as-randomized** (sensitivity) analyses. Similar to early intervention cohort, the patients in the delayed intervention cohort will be assigned to wave 1 or wave 2 (“pseudo”

³Not all OAC dispensings are captured in pharmacy claims, particularly, for warfarin due to some patients paying for medication out of pocket. INR tests are assumed indicative of OAC fills that were not billed through the claims. Four INR tests or values within a 12-month period will be used as a proxy since that is roughly the number of tests administered in the process of stabilizing dose.

wave assignments) depending on the difficulty in identifying the patient's provider (the intent is to handle them the same way as was done for the early intervention arm, for the modified intention-to-treat analysis). The follow-up for the delayed intervention patients will start on the date the wave 1 or 2 mailings took place for a given Data Partner's early intervention cohort. For both early and delayed intervention cohorts, any patients who die, are disenrolled, or get started on OAC between the randomization and early intervention mailing will be excluded from the analysis at each Data Partner. For both the early and delayed arms, exclusion criteria that are based on member medical history were assessed at the time of randomization. For the early intervention cohort, enrollment and treatment status were assessed at randomization for all and re-assessed at the wave 2 time point at some of the sites (this was at site discretion, in response to the lag between wave 1 and 2 mailings). The enrollment and treatment status of the delayed intervention cohort will be examined for eligibility at the same time point as the early intervention patients, meaning at the time of mailing per Data Partner, via the locked data (using the wave 1 and 2 dates).

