The proportion of patients actively on OAC at the end of follow-up will be summarized and compared between the early intervention and delayed intervention arms. Last Observation Carried Forward will be used if the patient is censored. To evaluate whether the early patient-level and provider-level educational intervention increases the proportion of patients being actively on OAC at the end of follow-up, we will calculate the odds ratio (i.e., the odds of an average patient in the early intervention group being actively on OAC at the end of follow-up as compared to the odds of an average patient in the delayed intervention group being actively on OAC at the end of follow-up) using logistic regression model adjusted for baseline risk factors listed in Appendix A Table A, with GEE to account for the correlation of responses among the patients from a same service provider. The odds ratio, 95% confidence interval (CI) and p-value will be presented to show whether there is a statistically significant difference in the proportion of patients who are actively on OAC at the end of follow-up between the early intervention and delayed intervention groups. Each Data Partner will run the SAS program(s) distributed by HPHCI, developed with the statistical team at Duke DCC, to perform logistic regression analysis on their cohort of patients and return the parameter estimate (SE), estimated odds ratio, 95% confidence interval (CI) and p-value, shown in Table 6 in Appendix A (there will be one for each Data Partner), to HPHCI. Meta-analysis methods with inverse-variance weighting on log scale will be used to integrate the results and obtain the estimate of the overall odds ratio, 95% confidence interval and p-value for entire study population.

4. Clinical Outcomes

Claims data (ICD-10-CM codes used for defining these outcomes are listed in Appendix C) will be used to define the following clinical outcomes:

- Hospitalization for ischemic stroke or unknown stroke
- Hospitalization for TIA
- Hospitalization for systemic embolism
- Hospitalization for ischemic stroke, TIA or systemic embolism
- Hospitalization for hemorrhagic stroke
- Hospitalization for any bleeding
- Hospitalization for ischemic or hemorrhagic stroke
- Hospitalization for ischemic or hemorrhagic stroke or systemic embolism
- Composite of ischemic stroke, hemorrhagic stroke, and hospitalization for any bleeding
- All-cause in-hospital death

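### The rule for being actively on OAC closes the INR route to any patient with an OAC fill, so a warfarin patient whose billed supply has lapsed but whose INRs continue is scored not active

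*Protocol*

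**What the plan says.** Protocol XV item 4 gives two routes to active status at the end of the one-year follow-up.

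- **Fill route.** The patient has "rivaroxaban, or warfarin medication fills that encompass the end of the study period", or an equivalent fill of another listed OAC.
- **INR route.** The condition comes first: "If there was no prescription fill for these medications, this will also include patients with 4 or". The threshold is thus at least four INRs during the study, and it counts only for a patient "who had an INR value measured within 60 days of the end of the approximately one-year follow-up".

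Item 2 of the same list (time to OAC start) opens its INR rule with the same condition: "If there was no prescription fill for these medications, but the patient had 4 or more INR values measured over the study period". Item 1, the primary endpoint, joins fills and INRs with a plain *or* and sets no such condition.

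Both documents explain why INRs are used. Protocol VI, footnote 1, says that "INR tests are assumed indicative of OAC fills that were not billed through the claims". SAP I.F, footnote 3, adds that capture is incomplete "particularly, for warfarin due to some patients paying for medication out of pocket".

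SAP II.D.3 says "The proportion of patients actively on OAC at the end of follow-up will be summarized and compared" between arms. It specifies an adjusted logistic model with GEE and last observation carried forward for censored patients. It does not define the status and does not mention INR. The title of SAP Table 6 restricts the analysis to patients with at least one day of treatment; the text of II.D.3 does not.

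**The concern.** The INR proxy exists because some warfarin use is invisible in pharmacy claims. One billed fill does not show that later fills were billed too. Under the literal rule, however, that one claim removes the only route by which later unbilled use could be seen. Of two patients with the same INR record, the one with more evidence of treatment is the one scored as off treatment.

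The condition has a clear purpose in item 2, where a claim date is a better start date than an INR date. It has no such purpose for a status at the end of follow-up.

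At stake is secondary endpoint 5, which asks whether treatment that was started is still in place. Continuing warfarin users would be counted as having lapsed.

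**Working it through.** **1. What the condition means.** The sentence puts no time limit on the absence of a fill. In item 2 the same words can only mean no fill at any time in the study period, because that item dates the first start. Read the same way in item 4, the rule is:

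active = (a fill spans the end) OR (no fill at all AND at least 4 INRs AND an INR within 60 days of the end).

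**2. The rule applied to test patients.** Follow-up ends on day 365. INRs fall every 30 days from day 40 to day 340, which makes 11 values, with days 310 and 340 inside the last 60 days. The comparison rule keeps the INR route open whether or not there was a fill.

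| Patient | Literal rule | INR route kept open |
|---|---|---|
| One 30-day warfarin fill on day 30, plus the INRs | not active | active |
| No fill, same INRs | active | active |
| One 90-day fill on day 300, same INRs | active | active |

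Only the first patient changes. The problem is confined to fills whose supply runs out before the end. Protocol XV item 3 also concedes that the duration of a warfarin supply is less well defined. A fully billed patient whose tablets outlast their nominal days can therefore fall into the same row.

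**3. Effect on each arm's level.** The documents give no figure for this endpoint and neither the warfarin share nor the unbilled share, so there is no stated result to reproduce. The inputs are:

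- Starts of 33% (delayed) and 38% (early), from Protocol XIV.A.1 and SAP I.G.1.
- Assumed: 20-40% of starters use warfarin.
- Assumed: 10-30% of those have some billed fills but unbilled supply at the end.

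Share of starters affected: 0.20 × 0.10 = 0.02 up to 0.40 × 0.30 = 0.12.

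Understatement of the proportion active, as a share of the whole arm:

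- Delayed: 0.33 × 0.02 = 0.66 points up to 0.33 × 0.12 = 3.96 points.
- Early: 0.38 × 0.02 = 0.76 points up to 0.38 × 0.12 = 4.56 points.

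These are upper limits for each pair of assumptions. Only patients with at least four INRs, one of them in the last 60 days, would be reclassified.

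**4. Effect on the comparison, with equal shares in both arms.** The arm difference falls by 0.76 − 0.66 = 0.10 up to 4.56 − 3.96 = 0.60 points, which is the 5-point difference in starts × 0.02 to 0.12.

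A second illustration assumes that 50% or 70% of starters are truly active at the end and that 1-10% of all starters are of the misclassified type.

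| Truly active | Difference, true | Difference at 1% | Difference at 10% |
|---|---|---|---|
| 50% | 19.0 − 16.5 = 2.5 | 18.62 − 16.17 = 2.45 | 15.2 − 13.2 = 2.0 |
| 70% | 26.6 − 23.1 = 3.5 | 26.22 − 22.77 = 3.45 | 22.8 − 19.8 = 3.0 |

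The planned measure is an odds ratio, and it moves little even at 10% (unadjusted):

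- 50% active: (0.19/0.81)/(0.165/0.835) = 1.19 becomes (0.152/0.848)/(0.132/0.868) = 1.18.
- 70% active: (0.266/0.734)/(0.231/0.769) = 1.21 becomes (0.228/0.772)/(0.198/0.802) = 1.20.

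**5. Table 6 denominator.** If at least one day of treatment means at least one dispensed day, patients who qualify only by INR leave the table. Everyone left has a fill and is barred from the INR route, so the proxy could never operate in this endpoint.

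**The case against.** **The wording may be loose rather than wrong.** The condition directly follows the clause on fills that span the end, and could be shorthand for no such fill. That reading would keep the INR route open. It cannot be ruled out, but the sentence does not say it, item 2 uses the same words for no fill at all, and the SAP does not settle it. One distributed program will run at five Data Partners, so the text has to state which is meant.

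**Preferring dispensing data is defensible.** Item 4 describes the endpoint as an active dispensing, so trusting claims where they exist favours specificity. Protocol footnote 1 says that four INRs is about the number needed to stabilise dose, so many warfarin starters would meet that count early. The reopened route would then rest largely on one late INR. This stands as a cost of the change and is a reason to show the result both ways.

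**Other measures exist.** Proportion of days covered also addresses lasting treatment. It too is based on fills, so it does not recover these patients.

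**Stronger readings that the documents do not support.** A reader might set the 0.7-4.0 points of understatement in the delayed arm against the planned 5-point difference and conclude that the effect could be swamped. The first is one arm's level and the second is a between-arm difference in another endpoint; the like-for-like figure is 0.1-0.6 points. A reader might also infer that the odds ratio is biased because patients prompted by a letter could differ in drug mix or billing. That is possible, but nothing in either document shows it. Nor do the documents say that warfarin fills are often unbilled: the Protocol says that not all dispensings are well captured, and the SAP refers to some patients.

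**Conclusion.** The point holds as a defect in an outcome definition. On its literal reading, which is also the one consistent with item 2, Protocol XV item 4 contradicts the stated purpose of the INR proxy, and SAP II.D.3 does not repair it.

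The direction is clear if one accepts the plan's own premise that continuing INRs indicate OAC use: the proportion active is understated in both arms. The size is unknown, because the 2-12% of starters is an assumption and an upper limit for its inputs. With equal misclassification, the contrast moves modestly towards no difference. Bias between arms would need a difference in warfarin share or billing that the documents do not show.

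The consequence is limited to one secondary endpoint. An affected patient still counts as having started OAC in the primary endpoint. The change is worth making because the rule misclassifies identifiable patients and is cheap to correct.

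**What to change.** 1. **Definition.** In Protocol XV item 4, replace the opening condition of the INR sentence, and write the same rule into SAP II.D.3: *If no OAC fill encompasses the assessment date, and the patient has either no OAC fill or a most recent OAC fill of warfarin*. Keep the existing INR test. The warfarin limit stops incidental INRs from counting patients who lapsed from other OACs as active.
2. **Assessment date.** State it once. Protocol XV item 4 refers to the end of one year, while SAP II.D.3 refers to the end of follow-up with last observation carried forward.
3. **Table 6.** Report in each arm the number active by fill and the number active by INR. Add the fill-only definition as a sensitivity analysis.
4. **Denominator.** Reconcile the restriction in the Table 6 title with SAP II.D.3, so that patients who qualify by INR are not dropped.

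The cost is a short text change in each document, one condition in the distributed program and a few table lines. The dispensing and INR data are already needed for the primary endpoint. The downside is that some patients who stopped warfarin but had a late INR for another reason will be scored active. The Table 6 split and the sensitivity analysis show how many patients depend on the INR route, and so bound that number.

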5. Health Care Utilization	177
III. REFERENCES	188
IV. APPENDIX	199
A. TABLES.....	199
B. CONSORT 2010 WORKSHEET FOR RANDOMIZED TRIALS.....	33
C. ICD-10 CODES FOR DEFINING CLINICAL OUTCOMES	3735
D. ANALYSIS METHODS FOR DISTRIBUTED NETWORKS	39
1. Meta-analysis	39
2. Case-centered Logistic Regression	39
3. Distributed Regression	39

I. OVERVIEW

This is the statistical analysis plan (SAP) for **IM**plementation of a randomized controlled trial to im**Pr**ove treatment with oral **AntiCoagulanTs** in patients with **A**trial **F**ibrillation (IMPACT-AFib) study. The purpose of this document is to provide an overview of the study design and study objectives, outline the types of analyses and data presentations relevant to the study objectives, and to provide a detailed description of the methods in which the statistical analyses will be conducted to meet protocol objectives. This plan is a supplement to the materials provided in the IMPACT-AFib protocol. This SAP does not contain all the protocol details and is intended to be read in conjunction with the full protocol. Only analytic decisions are documented here.

A. PRIMARY ENDPOINT

IMPACT-AFib is a prospective randomized controlled clinical trial that will evaluate whether a patient and provider education intervention increases the proportion of patients with atrial fibrillation (AF) who fill at least one oral anticoagulant (OAC) over the course of follow-up. Follow up is through the date on which at least 80% of eligible study participants have at least 12 months of follow-up time. As described in the protocol, there is an “early intervention” arm (who receive patient and provider mailings) and a “delayed intervention” arm (who receive provider mailings only, ~12 months after the early intervention mailings occur).

B. SECONDARY ENDPOINTS

We will evaluate the impact of the patient and provider education intervention on the endpoints listed below at the end of follow-up (i.e., the date on which at least 80% of eligible study participants have at least 12 months of follow-up time):

- The incidence rate of stroke or transient ischemic attack (TIA) hospitalizations
- The incidence rate of stroke hospitalizations
- The time to first OAC prescription fill
- The proportion of days covered by OAC prescription fills
- Proportion of patients actively on OAC at 12 months of follow-up
- The incidence rate of hospitalization for any bleeding
- All-cause in-hospital mortality rates¹
- Health care utilization, reported as counts of number of health care utilization events (outpatient visits, days hospitalized, number of emergency department visits, etc.)

Depending on the review of preliminary data, the primary endpoint and some secondary endpoints may be examined separately by warfarin and novel OAC. This will be descriptive only and will not include formal statistical testing.

C. EXPLORATORY ENDPOINTS

We will evaluate the effect of the early and delayed education interventions on the primary and secondary endpoints once at least 80% of eligible study participants have at least 24 months of follow-up time (the early intervention includes mailing to the patient and provider while the delayed intervention, at approximately 12 months follow-up, only includes a provider mailing). Note that we may

¹ Data for out of hospital mortality are not available

not conduct these analyses if the results of the primary outcome are null in the 12-month follow-up assessment. Therefore, this statistical analysis plan does not include the details of analyses for a 24-month assessment.

D. DATA SOURCE

The data used for the study are claims data from the five participating sites, transformed into the Sentinel Common Data Model. At the time of analysis, the data available in the Sentinel Distributed Database (i.e., those approved and in use for Sentinel routine surveillance activities) will be used to assess the primary and secondary endpoints.

As background, the identification and creation of the study cohort was based on the claims data in the Sentinel Distributed Database plus linked “fresh” data (i.e., about 1 month old) for pharmacy claims and enrollment information. The target population for the study was those members enrolled in the sites who did not have evidence of an OAC medication dispensing in the 12 months prior to randomization; the fresh and production data ensured we identified those eligible for the trial. The data used for routine Sentinel activities are several months old – hence the need for certain “fresh” data – and the date of the last available claims varies by site.

E. PATIENT INCLUSION CRITERIA

All inclusion and exclusion criteria were determined by claims data. For entry into the study, the following criteria **MUST** be met at the date of randomization:

1. Two or more diagnoses of AF (ICD-10-CM codes I48.0, 148.1, 148.2, 148.4, or I48.91; ICD-9-CM codes 427.3 or 427.31) at least one day apart and with at least one diagnosis within the last 12 months prior to the last date in the current approved data used for cohort identification
2. CHA₂DS₂-VASc score of 2 or greater at the time of the randomization (i.e., as of the last date in the current approved data used for cohort identification). The ICD-9/10-CM coding for CHA₂DS₂-VASc is shown in Table 1. The complete code list for inclusion and exclusion criteria is accessible on the Sentinel website (<https://www.sentinelinitiative.org/FDA-catalyst/projects/implementation-randomized-controlled-trial-improve-treatment-oral-anticoagulants-patients>).
3. Medical and pharmacy insurance coverage as identified via administrative claims data as of the date of randomization
4. Age 30 years or greater as of the last date in the current approved data used for cohort identification

Table 1. Coding for CHA₂DS₂-VASc components

	Component	Codes
C	Congestive heart failure (or left ventricular systolic dysfunction)	ICD-10-CM: I09.81, I11.0, I13.0, I13.2, I42.0, I42.5-I42.9, I43, I50.1, I50.20-23, I50.30–I50.33, I50.40-43; I50.9; ICD-9-CM: 398.91, 402.01, 402.11, 402.91, 404.01, 404.03, 404.11, 404.13, 404.91, 404.93, 425.2, 425.4, 425.5, 425.7, 425.9, 428.0-428.4, 428.20-428.23, 428.30-428.33, 428.40-428.43, 428.9
H	Hypertension: blood pressure consistently above 140/90 mmHg (or treated hypertension on medication)	ICD-10-CM: I10–I16 and subcodes, I67.4, N26.6; ICD-9-CM: 401-405, 401.0, 401.1, 401.9, 402.0, 402.1, 402.9, 403.0, 403.1,

	Component	Codes
		403.9, 404.0, 404.1, 404.9, 405.0, 405.1, 405.9, 437.2, 402.**, 403.**, 404.**, 405.**; CPT: 4050F
A₂	Age ≥75 years	
D	Diabetes Mellitus	ICD-10-CM: E08.31- E08.36, E08.3**, E08.40, E08.42, E08.51, E08.52, E08.59, E08.65, E09.31-E09.36, E09.3**, E09.40, E09.42, E09.51, E09.52, E09.59, E10.1–E13.9 and subcodes; ICD-9-CM: 250.*, 357.2, 362.0, 249.7*, 250.**, 362.0*, 366.41
S₂	Prior stroke or TIA or thromboembolism	ICD-10-CM: I60.**, I60.2, I60.4, I60.6-I60.9, I61.*, I62.9, I63.0*, I63.0**, I63.1*, I63.1**, I63.2*, I63.2**, I63.3*, I63.3**, I63.4*, I63.4**, I63.5*, I63.5**, I63.6, I63.8, I63.9, I69.00, I69.0**, I69.10, I69.1**, I69.30, I69.3**, I69.8** except I69.898, I69.9** except I69.998, S06.34, S06.34*A, and S063.34*D, S06.35, S06.35*A, and S063.35*D, S06.36, S06.36*A, and S063.36*D, S06.6, S06.6X*A, S06.6X*D, Z86.73, H34.00, H34.219, H34.239, H34.9, I67.82, I74.**, I74.2-I74.9, K76.3, N28.0, T81.718A, G45.8, G45.9; ICD-9-CM: 438.0-438.8, 852.0, 853.0, 433.*1, 434.*1, 438.1*, 438.2*, 438.3*, 438.4*, 438.5*, 438.81-428.85, 852.0*, 853.0*, V12.54, 444, 444.*, 444.**, 453.9, 573.4, 362.30-362.34, 434.00, 435, 435.8, 435.9; CPT: 34101, 34111, 34201, 34203
V	Vascular disease (e.g. peripheral artery disease, myocardial infarction, aortic plaque)	ICD-10-CM²: E08.51, E08.52, E09.51, E09.52, E10.51, E10.52, E11.51, E11.52, E13.51, E13.52, I21.0*, I21.1*, I21.2*, I21.3, I21.4, I22.*, I25.7, I25.70-I25.73, I25.70*, I25.71*, I25.72*, I25.73*, I25.79, I25.79*, I25.810, I73.8, I73.9, I77.1, T82.2, T82.21 and subcodes, Z95.820, Z95.82
A	Age 65–74 years	
Sc	Sex category (i.e. female sex)	

Patients are excluded if they meet any of the following criteria:

1. Evidence of OAC medication fill during the 12 months prior to randomization (the delayed intervention group’s treatment status will be assessed at the end of the 12-month follow-up period)

² Only ICD-10-CM codes are presented for the vascular disease component given size of the list; complete code list, which includes ICD-9-CM, ICD-10-PCS, ICD-9-PCS, CPT, and HCPCS codes, is available on the [Sentinel website](#).

2. Conditions other than AF that require anticoagulation such as ever having mechanical prosthetic valve, deep venous thrombosis, or pulmonary embolism prior to the last date in the current approved data used for cohort identification (“ever” is operationalized as -6000 days from the index AF code)
3. Pregnancy identified within 6 months of the last date in the current approved data used for cohort identification
4. Any known history of intracranial hemorrhage prior to the last date in the current approved data used for cohort identification
5. Hospitalization for any bleeding within the last 6 months of the last date in the current approved data used for cohort identification
6. Patients with recent P2Y12 antagonist use (i.e., clopidogrel, prasugrel, or ticagrelor within 90 days of prior to randomization)

F. STUDY DESIGN AND DURATION

As described in detail in the protocol, the study is a prospective, randomized, and open-label educational intervention trial. Patients with AF and a CHA₂DS₂-VASc score of 2 or greater were randomized in a 1:1 ratio to an early intervention cohort and a delayed intervention cohort within each participating health plan. The definition for OAC medication fill was an OAC medication dispensing or at least 4 INR tests in the claims data.³ The claims records of the patients randomized to the early intervention cohort were then linked to “fresh” (i.e., about 1 month old) pharmacy claims data at the time of randomization. Patients without evidence of an OAC medication fill during the 12 months prior to randomization were included in the patient-level and provider-level early educational intervention (patients randomized to this early intervention with evidence of an OAC medication fill during the 12 months prior to randomization were excluded from the trial). In addition to usual care, these patients and their providers received a one-time mailing at trial start. There were two waves of mailing for the early intervention cohort at most sites due to the practical challenges of claims data: the patients were assigned to wave 1 if they had a provider easily identified in the data (i.e., the provider associated with the most recent AF diagnosis is indeed an individual provider), and they were assigned to wave 2 if it was difficult to identify a provider (e.g., the first identified provider is actually a facility). Follow-up time started on the date of the respective wave 1 and wave 2 mailings for the early intervention patients.

The delayed intervention cohort will have received usual care over the initial study period. After the date on which at least 80% of all eligible study participants have at least 12 months of follow-up time, the treatment status of the delayed intervention group will be assessed via the Sentinel data available at that time, in addition to “fresh” pharmacy claims data. The providers of patients in the delayed cohort who did not receive OAC medication during the course of follow-up and still meet all inclusion criteria will receive the provider-only education intervention (patients will not receive the educational materials unless no provider can be identified for a mailing).

[figure not shown]
Details on the analyses are provided in Section II. Here we describe the data sources for the **modified intention-to-treat** (primary) and **as-randomized** (sensitivity) analyses. Similar to early intervention cohort, the patients in the delayed intervention cohort will be assigned to wave 1 or wave 2 (“pseudo”

³Not all OAC dispensings are captured in pharmacy claims, particularly, for warfarin due to some patients paying for medication out of pocket. INR tests are assumed indicative of OAC fills that were not billed through the claims. Four INR tests or values within a 12-month period will be used as a proxy since that is roughly the number of tests administered in the process of stabilizing dose.

wave assignments) depending on the difficulty in identifying the patient's provider (the intent is to handle them the same way as was done for the early intervention arm, for the modified intention-to-treat analysis). The follow-up for the delayed intervention patients will start on the date the wave 1 or 2 mailings took place for a given Data Partner's early intervention cohort. For both early and delayed intervention cohorts, any patients who die, are disenrolled, or get started on OAC between the randomization and early intervention mailing will be excluded from the analysis at each Data Partner. For both the early and delayed arms, exclusion criteria that are based on member medical history were assessed at the time of randomization. For the early intervention cohort, enrollment and treatment status were assessed at randomization for all and re-assessed at the wave 2 time point at some of the sites (this was at site discretion, in response to the lag between wave 1 and 2 mailings). The enrollment and treatment status of the delayed intervention cohort will be examined for eligibility at the same time point as the early intervention patients, meaning at the time of mailing per Data Partner, via the locked data (using the wave 1 and 2 dates).

Because the Sentinel Distributed Database will be used for analyses, and this information is refreshed approximately quarterly on different timetables for the different health plans, it is likely that when the required follow-up time is available for at least 80% of patients, there will be more than 12 months of follow-up for over 80% of patients. All participants' outcomes will be assessed using all possible person-time; patients will have different duration of follow-up and that will be accounted for in the analyses. Note that if the 24-month analysis is conducted, we will do that when at least 80% of members have at least 24 months of follow-up time.

A schematic diagram below shows the design of the early intervention period of the study: over the course of the follow-up, through the date on which at least 80% of eligible study participants have at least 12 months of follow-up time (see the protocol for the full study design and details):

[figure not shown]

*Baseline characteristics of delayed and early intervention cohorts will be taken from the same time point at randomization from a dataset that is archived at randomization, while exclusion criteria for evidence of OAC medication fill or P2Y12 antagonist use was determined at randomization for the early intervention cohort and approximately 12 months post-randomization for the delayed intervention cohort.

**All possible person-time will be used to assess participants' outcomes (patients will have different duration of follow-up).

For analysis, treatment status is at time of randomization or corresponding early intervention mailing; for the delayed intervention mailing it is prior to mailing.

A schematic diagram below shows the design of the delayed intervention portion of the study:

*All possible person-time will be used to assess participants' outcomes (patients will have different duration of follow-up).

For analysis, treatment status is at time of randomization or corresponding early intervention mailing; for the delayed intervention mailing it is prior to mailing.

[figure not shown]
G. SAMPLE SIZE JUSTIFICATION

1. Primary Endpoint

The following assumptions were used to determine the sample size and power for the primary endpoint assessing the proportion of AF patients with evidence of at least one OAC prescription fill through the date on which at least 80% of eligible study participants have at least 12 months of follow-up time:

1. 33% OAC initiation rate in the delayed intervention arm
2. 38% OAC initiation rate in the early intervention arm (5% absolute improvement in OAC initiation over the 33% OAC initiation expected in the delayed intervention arm over 1-year follow-up)
3. 1-year attrition rate: 30% dropout or lost-to-follow-up
4. Two-sided type I error rate of 0.05
5. Roughly 10,000 patients who meet the inclusion/exclusion criteria will yield more than 99% power to detect a 5% absolute difference

Power	Total sample size (2-arm)	Early Intervention	Delayed Intervention
90%	5610	2805	2805
95%	6910	3455	3455
99%	9718	4859	4859

2. Important Secondary Outcome of Stroke or TIA

A study with approximately 80,000 patients could provide reasonable power for stroke or TIA outcome under certain assumptions listed below:

- 1-year stroke or TIA rate: 18% among patients not treated with OAC
- 1-year stroke or TIA rate: 7% among patients treated with at least 1 OAC fill
- Duration of follow-up: 1 year
- 33% of delayed intervention patients will have at least 1 fill of OAC, meaning the 1-year stroke or TIA rate in the delayed intervention group would be 14.4%
- 1-year attrition rate: 30% dropout or lost-to-follow-up
- Two-sided type I error of 0.05
- If 38% of early intervention patients have at least 1 fill of OAC (meaning the 1-year stroke or TIA rate in the early intervention group would be 13.82%, i.e., an absolute reduction of 0.55%), the study will have 46% power to detect this 0.55% reduction. However, if 40.5% of early intervention patients have at least 1 fill of OAC (meaning the 1-year stroke or TIA rate in the

early intervention group would be 13.54%, i.e., an absolute reduction of 0.83%), the study will have 80% power to detect this 0.83% reduction.

8. The sample size has 80% power to detect a 0.5% absolute reduction in stroke, assuming a cumulative 1-year incidence of stroke of 4.2% in control (delayed intervention arm) patients and 3.7% in intervention (early intervention arm) patients. The assumption is that patients not on oral anticoagulation have an annual stroke rate of 5%, and stroke will be reduced by 50% (HR=0.5) in the treated (anticoagulated) population. The 80% power requires that 52% of early intervention arm patients are treated at 1-year as compared to 33% in the control arm.

II. STATISTICAL ANALYSIS

All primary analyses will be based on modified intention-to-treat (mITT) principle (i.e., all identified early intervention patients who met eligibility and were mailed the intervention will be included; using “pseudo” wave assignments, all identified delayed intervention patients who met eligibility at the time of corresponding early mailings will be included). Since the additional exclusions after randomization will be applied in the same way, using the same time points for both the early and delayed intervention groups, we expect there will be no effect from these additional exclusions on the randomization. The mITT analysis will include the following:

- Early intervention members who were mailed a letter, with follow-up beginning on the date of mailing (up to two dates per site and the dates varied by site).
- Delayed intervention members who were not on treatment at the date of mailing (wave assignments were made for the delayed as described earlier in section I.F) with follow-up beginning on that date.

An as-randomized analysis will be performed for an incident occurrence of the primary endpoint as a sensitivity analysis (using a washout of 365 days). Randomization occurred prior to treatment status assessment per the study design. Therefore, the as-randomized analysis will include people who were on treatment as well as others who were not truly eligible for the study (e.g., had incomplete or invalid addresses or had a “do not contact” status).

Potential sensitivity analysis for mITT analysis: There may be differential loss to follow up between the early and delayed intervention groups because some members did not have valid mailing addresses, though we did not assess the addresses of the members in the delayed intervention arm at the time of early intervention mailings. It is not possible to retrospectively ascertain the address status of the delayed intervention group as of the date on which mailing would have occurred for that group. We can estimate the magnitude by referring to the early intervention group, and in the early intervention group, we can compare the baseline characteristics and experience of the individuals who had no valid address to those who do.

